### ***D2 Dose Rationale and Risk/Benefits***

The RCT treatment arm of this study will use 2 grams of D-mannose powder dissolved in water once daily. The observational arm of this study will use either the same 2 grams of D-mannose powder daily as used in the RCT treatment arm or two 500 mg D-mannose capsules every 12 hours (for a total of 2 grams every day).

The prior studies previously mentioned evaluating D-mannose each used a different dose. The first RCT used 2 grams of D-mannose dissolved in 200 ml water [9]. In the other RCT, participants were started on D-mannose 1 gram three times daily for two weeks (as treatment for acute urinary tract infection) followed by 1 gram twice daily [15].

To date the FPMRS division clinical practice has been to recommend either two 500 mg capsules of D-mannose twice daily or 2 grams (1 teaspoon of powder) dissolved in water once daily. The powdered D-mannose will be used for the randomized, controlled trial as pure D-mannose can be dissolved in water and administered without the additional additives required to encapsulate D-mannose. Using the powdered D-mannose limits the possible additional side effects due to additives. For the observational arm, the powdered D-mannose will be strongly recommended, but patients will be allowed to purchase either the powder or capsules and formulation will be tracked.

---

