## **E Study Design**

### ***E1 Overview or Design Summary***

In the RCT portion of the study, we will enroll 120 postmenopausal female patients with rUTI (either new patients or existing patients with a new diagnosis of rUTI) as defined by  $\geq 2$  culture-proven UTI episodes in the last six months or  $\geq 3$  culture-proven UTI episodes in the last twelve months. Each subject must have at minimum a documented culture-proven UTI with a D-mannose susceptible microbe. Subjects will be randomized to vaginal estrogen therapy (VET) plus D-mannose versus VET alone and will be followed for 90 days. All RCT participants will have a minimum four-week run-in period with VET prior to study day 1. Subjects previously on VET will not require a run-in period as long as the four-week minimum on VET has been met. According to the North American Menopause Society, the effect of vaginal estrogen therapy is rapid and can generally be observed within four weeks of treatment onset with cream, ring, or tablet forms of vaginal estrogen therapy [19]. Subjects randomized to treatment with D-mannose will receive their D-mannose as part of the study so that D-mannose treatment is controlled for the use of pure D-mannose powder. A study period of 90 days was determined as an adequate study period as prior publications have demonstrated that UTI recurrence most commonly occurs within two months [9, 20, 21].

In the observation arm of the study, we will enroll 60 postmenopausal women with rUTI (either new patients or existing patients with a new diagnosis of rUTI) as defined by  $\geq 2$  culture-proven UTI episodes in the last six months or  $\geq 3$  culture-proven UTI episodes in the last twelve months. Each study participant must have at minimum a documented culture-proven UTI with a D-mannose susceptible microbe. These patients must meet all of the same inclusion and exclusion criteria as the randomized, controlled trial subjects with the exception of not using VET due to a contraindication or preference not to use VET. Participants in this arm of the study will be followed for three months after starting D-mannose. For the observational arm, the powdered D-mannose will be strongly recommended, but patients will be allowed to purchase either the powder or capsules and formulation will be tracked.

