## **2.b Exclusion Criteria**

For the RCT arms of the study, the exclusion criteria are as follows:

- a. Not postmenopausal
- b. Currently on daily antibiotic UTI prophylaxis
  - i. If this is the only exclusion criteria met, a woman could be cleared for inclusion in study/enrollment after a 2 week washout period occurs prior to inclusion in the study (RCT or Observational arm)
- c. Complicated UTIs
  - i. known renal tract anomaly
  - ii. inability to empty bladder due to neurologic causes
  - iii. performs self-catheterization or has an indwelling catheter
- d. Patients with incomplete bladder emptying (defined as PVR > 150 cc when minimal voided volume is >150 cc)
- e. Known contraindication to VET unless approved by patient's oncologist, oncologic surgeon, or primary care physician
  - i. History of or current endometrial cancer without approval of patient, patient's oncologist, oncologic surgeon, or primary care physician to use vaginal estrogen after counseling
  - ii. History of estrogen sensitive breast cancer without approval of patient, patient's oncologist, oncologic surgeon, or primary care physician to use vaginal estrogen after counseling
- f. History of interstitial cystitis/painful bladder syndrome
- g. Urothelial cancer
- h. Non-English speaking
- i. Enrolled in other clinical trials for UTIs
- j. Currently using D-mannose or Methenamine for UTI prevention

Exclusion criteria for the Observational arm of the study are the same with the exception of item 'e.' above (known contraindication to VET) as participants will not be on vaginal estrogen therapy.

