### **2.d Subject Recruitment Plans and Consent Process**

All new or newly diagnosed women with rUTIs receiving care at the Washington University Physicians Women's Center for Bladder and Pelvic Health who meet screening criteria will be approached. Existing rUTI patients that are not currently using D-mannose may also be approached. Enrollment may occur at any of the practice's four outpatient locations (Washington University Physicians' offices at: Center for Outpatient Health, Missouri Baptist Medical Center Women's Wellness Center, Center for Advanced Medicine - South County, and Barnes Jewish West County Medical Building). This study will involve only adult, postmenopausal women as rUTI predominantly affect this population. Recurrent UTI in men would be considered complicated and would not be addressed with a prophylactic treatment like d-mannose. In addition, men do not go through menopause and do not have a vagina and would thus not be treated with VET. Women meeting study criteria will be approached by a member of the research team for consent at the conclusion of the clinical visit during which the patient is screened eligible for the study. Women who meet RCT eligibility criteria except for a minimum of four weeks of VET use but are being started on VET for clinical indications will followup in approximately four weeks for a routine follow up clinical visit. These patients will be offered enrollment in the study at that time if they have been using VET for a couple weeks even if they aren't at the four week mark yet. However, their study day one cannot occur until they have been using VET for four weeks.

Eligible women interested in the study will have the study explained to them, the consent reviewed, and questions reviewed in a confidential manner in a private room. If the potential research participant would like to take the consent home with them to review before their next office appointment that will be allowed.

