## 2.f Risks and Benefits

D-mannose is a nutraceutical sold over the counter solely for the prevention of UTI. It falls under the category of dietary supplements regulated by FDA under the Dietary Supplement Health and Education Act of 1994 (DSHEA) [24]. This is a different set of regulations than the regulations used for conventional food and drug products [24]. Risks associated with D-mannose use are believed to be mainly related to gastrointestinal side effects (bloating, loose stool, and diarrhea). Other possible side effects can include but are not limited to hypersensitivity or allergic reactions (acute skin or pulmonary changes). These side effects would be the same for subjects enrolled in this study as for patients not enrolled in this study that we recommend D-mannose prophylaxis to on a daily basis. Other potential risks of the study include participants may feel uncomfortable or be inconvenienced by filling out study related papers. They may prefer to obtain treatment for UTI-like symptoms from an urgent care or other outside provider. However, all rUTI patients in our office (no matter if enrolled in the study or not) are instructed to call our office when they experience UTI-like symptoms since our clinical practice is to obtain (when possible) urine cultures prior to initiating treatment and to have our patients followed primarily through our office for their urinary tract infections.

A potential benefit is the decreased incidence of rUTI among patients randomized to D-mannose in the randomized, controlled trial portion of the study or patients in the observational arm of the study. Otherwise, benefits for the participant are no different than if they were recommended D-mannose as part of their routine clinical care as a patient without being enrolled in the study. There is a global benefit of increased knowledge surrounding the utility of non-antibiotic prophylaxis for rUTI.

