### **3.d Preparation and Administration of Study Drug**

For the treatment arm of the RCT, the D-mannose powder will be ordered and distributed by the research team. The study team has selected NOW D-mannose pure powder as the D-mannose to be used in the RCT. The manufacturer label will be covered up/removed and a study label stating contents of a nutraceutical will be used to maintain patient blinding to which nutraceutical is being used.

For both arms of the RCT, the VET may be renewed or prescribed by a physician on the research team per routine clinical care. The patient will then pick up their prescription (vaginal cream, ring, or tablet) from their pharmacy of choice for continued use.

For the Observational arm of the study we will recommend the powdered D-mannose, but since participants will be purchasing their own D-mannose in the Observational arm they will be instructed to purchase either NOW D-mannose pure powder or NOW D-mannose 500 mg capsules. NOW will be the only brand patients are instructed to purchase, and example labels will be available for viewing by participants in the Observational arm to confirm they purchase the recommended D-mannose. We will communicate with the participants after they purchase their D-mannose of choice to record if powder or tablet and brand/manufacturer.

Medication (D-mannose, VET) will be self-administered by the patient. For patients using VET they will continue to use their VET as previously prescribed prior to enrollment in this study. On study day 1, if the patient is in an arm using D-mannose they will begin self administering D-mannose according to the instructions on the patient information handout. These instructions are as follows:

- **Powder specific instructions:** Dissolve one (1) teaspoon of the nutraceutical powder in at least 200 ml of water one time a day. (200 ml of water = 6.7 fluid ounces). Please attempt to take doses of the nutraceutical powder dissolved in water approximately 24 (twenty-four) hours apart. It is ok if you use a larger volume of water to dissolve the powder, but do not use any less than 200 ml of water. You MUST drink all of the water that the powder is dissolved in.”

---

- Capsule specific instructions: Take two 500 mg capsules (total of 1000 mg dose) every 12 hours.”

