## **F Study Procedures**

### ***F1 Screening for Eligibility***

Prior to a new patient appointment, all patients referred for or with a chief complaint of frequent or recurrent urinary tract infections will be prescreened by a member of the research team. Items from the patient's chart or clinical records that may be used to identify potential participants for recruitment include: name, date of birth, date of appointment, reason for appointment, history of UTI, medication history, menopausal status, if patient has a known renal tract anomaly, neurogenic bladder, performs self-catheterization or has indwelling catheter, history of incomplete bladder emptying, history of contraindication to vaginal estrogen therapy including but not limited to current endometrial cancer or breast cancer without approval of patient's oncologist, surgical oncologist, or primary care physician, history of interstitial cystitis/painful bladder syndrome, history of urothelial cancer, and primary language spoken.

For patients that are existing patients of FPMRS division but with a new diagnosis of rUTI, the member of the research team that diagnoses the patient with rUTI will notify the members of the research team performing screening that the existing patient will be coming to the office for a new diagnosis of rUTI. Prior to the patient's appointment, she will be prescreened by a member of the research team. If the patient appears eligible from screening then any missing information will be obtained during routine clinical care during the patient's appointment to complete the screening process. If a patient is an existing patient of the FPMRS division with rUTI and not already using D-mannose, then they may be screened when they attend a routine clinical appointment with a member of the research team.

If a patient is noted to be eligible during an office visit (i.e. the new diagnosis of recurrent urinary tract infection was made during an appointment) and therefore the patient was not prescreened prior to the appointment, then a member of the research team will be notified as soon as possible to complete the screening process to see if a patient is eligible for study participation.

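### Eligibility tests only current D-mannose use, so a woman with an earlier reaction to it can be randomised and re-exposed under a label that hides its name

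*Combined protocol and SAP*

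**What the plan says.** Exclusion j in E2 2.b reads "Currently using D-mannose or Methenamine for UTI prevention". It applies to the RCT and, because only item e is waived there, to the observational arm as well. Nothing else in 2.a or 2.b concerns D-mannose history.

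The recruitment section (2.d) says "Existing rUTI patients that are not currently using D-mannose may also be approached". F1 says "If a patient is an existing patient of the FPMRS division with rUTI and not already using D-mannose, then they may be screened". E1 is narrower and describes the population as "either new patients or existing patients with a new diagnosis of rUTI".

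On how likely earlier exposure is, D2 states "To date the FPMRS division clinical practice has been to recommend either two 500 mg capsules of D-mannose twice daily or 2 grams" and 2.f speaks of "patients not enrolled in this study that we recommend D-mannose prophylaxis to on a daily basis". E3 3.a adds that the product can be bought without prescription.

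On risk, 2.f describes mainly gastrointestinal effects and then names "hypersensitivity or allergic reactions (acute skin or pulmonary changes").

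On masking, 3.d says that in the RCT treatment arm "a study label stating contents of a nutraceutical will be used to maintain patient blinding to which nutraceutical is being used". 3.g repeats this, and G5 says RCT patients are to stay unaware of which nutraceutical is studied.

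**The concern.** In a trial where the product is named, a woman who has reacted to it before can recognise the name and decline. Here that self-protection is removed by design, and no eligibility criterion takes its place. The plan names hypersensitivity as a possible harm but does not carry it into the exclusions.

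Interpretation is also at stake. C2 makes side effects, and discontinuation because of them, a secondary aim. G3 estimates both as a simple proportion of the D-mannose plus VET arm. Among women who have ever used D-mannose, exclusion j removes those still taking it and admits those who stopped. If some stopped because they could not tolerate it, they enter that proportion, and the plan has no stated means of identifying them. Women who stopped for lack of benefit would weaken the primary contrast in the same unrecorded way.

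**Working it through.** **Reading the text**

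1. Eligibility: 2.b, 2.d and F1 each ask whether the woman uses D-mannose now. None asks whether she used it before, when she stopped, or why.
2. Entry route: E1 covers new patients and existing patients newly diagnosed. 2.d and F1 also let in existing rUTI patients who are not on D-mannose. These do not agree. E1 alone would not close the gap, since a new patient may have bought the product herself.
3. Risk: 2.f lists allergic reactions.
4. Masking: 3.d, 3.g and G5 hide the name, but only in the RCT treatment arm. Observational participants buy the named product (3.d), so hidden re-exposure cannot arise there.
5. Safeguards: 3.g leaves the research team unblinded to the study drug. F1 includes medication history among the chart items that staff can use. 2.h lets an investigator end participation to protect a woman from excessive risk. None of these is linked to a rule on D-mannose history.

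Taken together, a woman with an earlier reaction meets every written criterion. With 1:1 allocation she has about an even chance of receiving the product unnamed.

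**The planned sample size (G1)**

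Inputs from G1: 45% risk on VET alone, 20% on D-mannose, 10% dropout, 60 per arm. G1 states neither alpha nor power. I assume two-sided 0.05 and 80%.

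n = [1.960 √(2 p̄(1−p̄)) + 0.842 √(p₁(1−p₁) + p₂(1−p₂))]² / (p₁−p₂)², with p̄ = 0.325:

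n = [1.960 √0.43875 + 0.842 √0.4075]² / 0.25² = 53.9, so 54 per arm. Then 54 / 0.90 = 60.

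The planned 60 is reproduced exactly. Power at 54 evaluable per arm is 80.1%.

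**Illustration of dilution**

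The documents give no share of former users. Assume a fraction f of both arms are former non-responders in whom D-mannose does nothing, so their risk stays at 45%. Treatment-arm risk is then 0.20(1−f) + 0.45f.

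| f (assumed) | Treatment-arm risk | Difference (points) | Power, 54 per arm | n per arm for 80%, after dropout |
|---|---|---|---|---|
| 0 | 20% | 25 | 80.1% | 60 |
| 5% | 21.25% | 23.75 | 75.3% | 68 |
| 10% | 22.5% | 22.5 | 70.1% | 77 |
| 20% | 25% | 20 | 58.9% | 99 |
| 30% | 27.5% | 17.5 | 47.2% | 132 |

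If a fraction f of the 120 randomised women were former users of any kind, about 60f would be allocated to treatment: 6 at 10%, 12 at 20%. Those with an earlier reaction would be some unknown part of that number.

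**The case against.** The strongest reply is that re-exposure would have to get past people who know the product. The research team is unblinded, screens within its own division, and can see medication history. During the study there are weekly symptom texts with call-back and a six-week call (3.e). The enrolment visit form and screening log are listed as attachments (K3) and may already ask about past use. The plan also describes the expected risk as low: mainly gastrointestinal effects (2.f), rash or itching rare (F3 3.d), and a dose well below the one linked to symptoms in 10% of subjects (D2).

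Most of this stands as mitigation. It does not close the gap: staff who found an earlier reaction would have no criterion to apply, and follow-up contacts act only after exposure.

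Three stronger readings are tempting, and the documents do not support them.

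- A reader might infer that former non-responders bias the primary comparison. They do not. Randomisation spreads them across arms in expectation; they change the population effect and reduce power.
- A reader might infer that the sample is bound to contain former users who stopped for side effects or failure. Routine recommendation makes this plausible, but no passage gives a number or a reason for stopping.
- A reader might infer that a washout, or an exclusion of earlier non-responders, is needed. The two-week washout in exclusion b concerns antibiotics, and no passage supports a carry-over period for D-mannose. Excluding earlier failures while admitting former users who tolerated or benefited from it would enrich the sample in the product's favour and lower the side-effect incidence that C2 sets out to measure. Failure without VET also does not establish failure with VET, and the additive effect is the trial's question.

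**Conclusion.** The point holds in a narrow form. As written, eligibility permits a woman with an earlier reaction or intolerance to D-mannose to be randomised and, in the treatment arm, given it unnamed. Unblinded staff and an optional look at medication history reduce this risk without a rule behind them. This conclusion rests on the text alone and needs no assumption about how many former users there are.

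The frequency is unknown and may be low. The fall in power from about 80% to 70% or 59% is illustrative only. It assumes 80% power and two-sided 0.05 at baseline, fractions of 10% or 20% that have no source, and no benefit at all in former non-responders. It should not drive the importance given to the point.

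This is an inexpensive improvement to safety and interpretability, not a flaw that invalidates the comparison. Confidence is medium: high for the wording of the criterion, lower for practice, because the enrolment and consent forms could not be examined.

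**What to change.** 1. Reconcile the eligibility text (2.b exclusion j, 2.d, F1) with the hypersensitivity risk in 2.f and the masked label in 3.d, 3.g and G5, so that eligibility addresses an earlier reaction or intolerance to D-mannose. The exact clinical rule is for the sponsor to decide.
2. At enrolment, record earlier D-mannose use, how recent it was and why it stopped. Ask within a list of several supplements, so that the question does not reveal the study product. C3 already commits to recording other agents, so the item has a natural place.
3. Prespecify in G3 a sensitivity analysis of the primary outcome and of side effects and discontinuation by earlier D-mannose use.
4. Make E1 agree with 2.d and F1 on whether existing rUTI patients without a new diagnosis may enter.

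The cost is protocol wording, one form item, a small additional analysis and a few lost candidates in a trial that G2 says is already recruiting more slowly than expected.

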## **2.c Ethical Considerations**

### Inclusion of Women and Minorities

The patient sample for this study is limited to women as rUTI is most common in postmenopausal women. Men with UTI are by definition complicated and would not meet the inclusion criteria. In addition, men do not go through menopause and do not have a vagina and would thus not be treated with VET. All four locations of the Washington University Physicians

---

Women's Center for Bladder and Pelvic Health are located in the St. Louis Metropolitan area, which is the 20th largest metropolitan statistical area in the nation [22]. As of 2015, of the 2.8 million people in the St Louis Metropolitan Area, approximately 510,000 individuals identify as Black and an additional 81,000 identify as Hispanic [22]. The main office location for the Women's Center for Bladder and Pelvic Health is located in St. Louis City where approximately 50% of residents are Black or African American [23]. Six percent of the citizens of the St. Louis Missouri and Illinois Metropolitan area are non-English language speakers, which is considerably lower than the national average of 21.5% [22]. For this reason, even though this study is limited to English speaking patients, we do not anticipate this will negatively impacting the racial/ethnic minority representation in our study.

